4.4. Last Product Use Visit (LPUV) or Early Discontinuation Visit

Note: *LPUVs will be calculated from the enrolment visit as baseline date. This scheduled visit has a window period of \pm 7 days.*

- a. Update locator and menses information as necessary.

- b. Obtain and record any AE and concomitant medication information since the last visit.

- c. Perform a pelvic examination (refer to Section 5.9). If the pelvic examination indicates abnormal findings, e.g., any symptoms or evidence of genital infections, abrasions, ulcerations, etc., provide the participant with or refer the participant for appropriate treatment.

NOTE: *If the participant is menstruating at this visit, the pelvic examination may be conducted as per investigator and participant discretion. If this is not possible, the participant will be asked to return 2 days after completion of menstruation.*

- d. Record possible social harms (refer to Section 10.2)
- e. Perform a general physical examination (refer to Section 5.8 for a description of the elements required in the general physical examination).
- f. Instruct the participant to remove the vaginal ring. Perform IP accountability and visual inspection of the returned ring(s). Returned rings may be analysed for residual amounts of dapivirine and will be stored until shipment to the analytical laboratory.
- g. Collect and review the diary card(s).
- h. Administer the Participant Questionnaire (refer to Section 5.16).
- i. Provide HIV/STI risk reduction counselling; including provision of male condoms if the participant wishes to receive them (refer to Section 5.3.2).
- j. Perform contraceptive counselling and provide contraceptives, if necessary (refer to Section 5.5).
- k. Perform urine pregnancy test. Refer pregnant women to local prenatal clinic for support services (refer to Section 5.6).
- l. Collect cervicovaginal swabs for STI testing (refer to Sections 5.11.1).
- m. Provide STI treatment if needed (refer to Section 5.11.2).
- n. Provide HIV pre- and post-test counselling (refer to Section 5.3.1).
- o. Perform HIV rapid testing as detailed in Section 5.4.3.
- p. Collect a blood specimen by venepuncture for storage for possible HIV viral genotype resistance and HIV-RNA PCR testing (Blood volume specified in Appendix C).
- q. Collect blood (Blood volume specified in Appendix C) and vaginal fluid samples (refer to Section 5.17) for possible measurement of dapivirine concentrations.

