5.11. STI Testing and Management

5.11.1. STI Testing

Cervicovaginal samples will be collected for STI testing at screening and the LPUV, or any other trial visit if clinical indicated. All participants will be evaluated for *Trichomonas vaginalis* (TV), *Neisseria gonorrhoeae* (NG) and *Chlamydia trachomatis* (CT). At screening, blood will be collected by venepuncture for Syphilis (RPR) testing (Blood volume specified in Appendix C). TPHA/TPPA testing will be performed if the RPR is reactive.

Additional descriptive information regarding specimen collection to test for STIs and processing of all tests will be detailed in the Laboratory Manual, as part of the SOM.

NOTE: Documentation will be made in applicable CRFs for all cervicovaginal samples obtained in the presence of cervicovaginal blood.

The investigator or appropriately qualified and trained trial staff as designated by the investigator will review all results, including rapid and laboratory tests, and the review will be documented by the reviewer on the original laboratory report itself.

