5.1 Safety Population

The safety population will include all participants who were enrolled, and received and inserted at least one Dapivirine Vaginal Ring

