10.5 STI assessments

10.5.1 Assessments

Cervicovaginal samples will be collected for STI testing (Trichomonas, Gonorrhoea, and Chlamydia) at Screening and at the last product use visit, or any other trial visit as clinically indicated. At Screening, blood will be collected for Syphilis (RPR) testing. TPHA/TPPA testing will be performed if the RPR is reactive.

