SIL-low grade	n (%) ^a	X (X.X)	X (X.X)	X (X.X)	...	X (X.X)	X (X.X)	X (X.X)
ASC-H	n (%) ^a	X (X.X)	X (X.X)	X (X.X)	...	X (X.X)	X (X.X)	X (X.X)
SIL-high grade	n (%) ^a	X (X.X)	X (X.X)	X (X.X)	...	X (X.X)	X (X.X)	X (X.X)
AGC	n (%) ^a	X (X.X)	X (X.X)	X (X.X)	...	X (X.X)	X (X.X)	X (X.X)
AGC-favor neoplastic	n (%) ^a	X (X.X)	X (X.X)	X (X.X)	...	X (X.X)	X (X.X)	X (X.X)
Cancer	n (%) ^a	X (X.X)	X (X.X)	X (X.X)	...	X (X.X)	X (X.X)	X (X.X)
Other findings	n (%) ^a	X (X.X)	X (X.X)	X (X.X)	...	X (X.X)	X (X.X)	X (X.X)

^a Percentages are calculated out of the number of participants in the safety population per centre and IPM 027 treatment

Centre 01: Madibeng Centre for Research (MCR); Centre 02: MatCH Research Unit (MRU); Centre 04: Qhakaza Mbokodo (QM);

Centre 06: MRC/UVRI & LSHTM Uganda Research Unit (MRC/UVRI); Centre 07: Desmond Tutu HIV Foundation (DTHF), Masiphumelele; Centre 08: Ndlovu Care Group (NCG)

Table 14.3.7.3
Sexually Transmitted Infections
Safety Population

Visit Test	Statistic	Centre 01				All Centres		
		IPM 027 Dapivirine (N=XXX)	IPM 027 Placebo (N=XXX)	IPM 032 Overall (N=XXX)	...	IPM 027 Dapivirine (N=XXX)	IPM 027 Placebo (N=XXX)	IPM 032 Overall (N=XXX)
Screening	n (%) ^a	X (X.X)	X (X.X)	X (X.X)	...	X (X.X)	X (X.X)	X (X.X)
Any STI*	n (%) ^a	X (X.X)	X (X.X)	X (X.X)	...	X (X.X)	X (X.X)	X (X.X)
Chlamydia positive	n (%) ^a	X (X.X)	X (X.X)	X (X.X)	...	X (X.X)	X (X.X)	X (X.X)
Syphilis RPR	n (%) ^a	X (X.X)	X (X.X)	X (X.X)	...	X (X.X)	X (X.X)	X (X.X)
Gonorrhoea positive	n (%) ^a	X (X.X)	X (X.X)	X (X.X)	...	X (X.X)	X (X.X)	X (X.X)
Trichomonas positive	n (%) ^a	X (X.X)	X (X.X)	X (X.X)	...	X (X.X)	X (X.X)	X (X.X)
Blood present during collection of cervico-vaginal samples	n (%) ^a	X (X.X)	X (X.X)	X (X.X)	...	X (X.X)	X (X.X)	X (X.X)
LPUV	n (%) ^a	X (X.X)	X (X.X)	X (X.X)	...	X (X.X)	X (X.X)	X (X.X)
Any STI*	n (%) ^a	X (X.X)	X (X.X)	X (X.X)	...	X (X.X)	X (X.X)	X (X.X)
Chlamydia positive	n (%) ^a	X (X.X)	X (X.X)	X (X.X)	...	X (X.X)	X (X.X)	X (X.X)
Syphilis confirmatory test	n (%) ^a	X (X.X)	X (X.X)	X (X.X)	...	X (X.X)	X (X.X)	X (X.X)
TPHA/TPPA	n (%) ^a	X (X.X)	X (X.X)	X (X.X)	...	X (X.X)	X (X.X)	X (X.X)
Gonorrhoea positive	n (%) ^a	X (X.X)	X (X.X)	X (X.X)	...	X (X.X)	X (X.X)	X (X.X)
Trichomonas positive	n (%) ^a	X (X.X)	X (X.X)	X (X.X)	...	X (X.X)	X (X.X)	X (X.X)
Blood present during collection of cervico-vaginal samples	n (%) ^a	X (X.X)	X (X.X)	X (X.X)	...	X (X.X)	X (X.X)	X (X.X)

LPUV = Last product use visit

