^a Percentages are calculated out of the number of participants in the safety population per centre and IPM 027 treatment

* Includes Chlamydia, Gonorrhoea, Syphilis and Trichomonas

Centre 01: Madibeng Centre for Research (MCR); Centre 02: MatCH Research Unit (MRU); Centre 04: Qhakaza Mbokodo (QM);

Centre 06: MRC/UVRI & LSHTM Uganda Research Unit (MRC/UVRI); Centre 07: Desmond Tutu HIV Foundation (DTHF), Masiphumelele; Centre 08: Ndlovu Care Group (NCG)

Table 14.3.7.4
Immediately Reportable Events
Safety Population

Event	Statistic	Centre 01				All Centres		
		IPM 027 Dapivirine (N=XXX)	IPM 027 Placebo (N=XXX)	IPM 032 Overall (N=XXX)	...	IPM 027 Dapivirine (N=XXX)	IPM 027 Placebo (N=XXX)	IPM 032 Overall (N=XXX)
Number of participants confirmed pregnant	n (%) ^a	X (X.X)	X (X.X)	X (X.X)	...	X (X.X)	X (X.X)	X (X.X)
Number of participants confirmed pregnant	PY	XXX	XXX	XXX	...	XXX	XXX	XXX
Total number of person-years		XX.X	XX.X	XX.X		XX.X	XX.X	XX.X
Pregnancy incidence rate (per 100 person-years)								
Number of confirmed pregnancies	n	XXX	XXX	XXX	...	XXX	XXX	XXX
Pregnancy report								
Number of confirmed pregnancies	n	XXX	XXX	XXX	...	XXX	XXX	XXX
Contraceptive method at the time of positive pregnancy test								
Oral contraceptive	n (%) ^a	X (X.X)	X (X.X)	X (X.X)	...	X (X.X)	X (X.X)	X (X.X)
Transdermal contraceptive patch	n (%) ^a	X (X.X)	X (X.X)	X (X.X)	...	X (X.X)	X (X.X)	X (X.X)
Long acting injectable progestins	n (%) ^a	X (X.X)	X (X.X)	X (X.X)	...	X (X.X)	X (X.X)	X (X.X)
Etc.								
Pregnancy outcome								
Full term live birth (≥ 37 weeks)	n (%) ^b	X (X.X)	X (X.X)	X (X.X)	...	X (X.X)	X (X.X)	X (X.X)
Premature term live birth (< 37 weeks)	n (%) ^b	X (X.X)	X (X.X)	X (X.X)	...	X (X.X)	X (X.X)	X (X.X)
Stillbirth/intrauterine fetal demise (≥ 20 weeks)	n (%) ^b	X (X.X)	X (X.X)	X (X.X)	...	X (X.X)	X (X.X)	X (X.X)
Etc.								
HIV-1 Seroconverters	n (%) ^a	X (X.X)	X (X.X)	X (X.X)	...	X (X.X)	X (X.X)	X (X.X)

HIV-1 = Human immunodeficiency virus type 1

PY = (Date of last ring removal – Date of first ring insertion + 1)/365.25

Percentages are calculated out of the number of participants (per centre and IPM 027 treatment)^a In the safety population ^b Total pregnancy outcomes

Centre 01: Madibeng Centre for Research (MCR); Centre 02: MatCH Research Unit (MRU); Centre 04: Qhakaza Mbokodo (QM);

Centre 06: MRC/UVRI & LSHTM Uganda Research Unit (MRC/UVRI); Centre 07: Desmond Tutu HIV Foundation (DTHF), Masiphumelele; Centre 08: Ndlovu Care Group (NCG)

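### In Table 14.3.7.3 the screening and last-product-use 'Any STI' percentages are not comparable: syphilis is scheduled for testing only at screening, and untested women count as negative

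*SAP*

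**What the plan says.** SAP section 10.5.2 presents STI results for screening and LPUV in Table 14.3.7.3. Three rules govern the table.

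- **Composite.** A single footnote covers the 'Any STI' row in both visit blocks: "Includes Chlamydia, Gonorrhoea, Syphilis and Trichomonas".
- **Denominator.** Footnote a applies to every row: "Percentages are calculated out of the number of participants in the safety population per centre and IPM 027 treatment". SAP section 5.1 defines that population as "all participants who were enrolled, and received and inserted at least one Dapivirine Vaginal Ring". Neither attending LPUV nor having an STI result is required.
- **Test schedule.** SAP section 10.5.1 states "At Screening, blood will be collected for Syphilis (RPR) testing", and protocol section 5.11.1 agrees: "At screening, blood will be collected by venepuncture for Syphilis (RPR) testing". Protocol Appendix A marks RPR under screening only, and Appendix C lists RPR blood at screening only. The confirmatory test is a reflex: "TPHA/TPPA testing will be performed if the RPR is reactive". The LPUV procedures in protocol section 4.4 list cervicovaginal swabs and no RPR.

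The syphilis row in the screening block is RPR. In the LPUV block it is "Syphilis confirmatory test" (TPHA/TPPA), at a visit with no scheduled RPR to trigger it.

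Under protocol section 4.7, a woman who misses LPUV should have her STI test at the Exit Visit. The table has no Exit Visit block, and the SAP does not say whether that result is carried into the LPUV block.

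**The concern.** A reader will set the two visit blocks against each other, since the table summarises STI tests before and at the end of use of a vaginal product. Two features of the shell, unrelated to infection, act on that comparison. The LPUV composite loses one of its four components by schedule. Women with no LPUV result stay in the denominator and so count as uninfected. Each feature lowers the LPUV figure. Unless screening results are also missing, a constant prevalence is displayed as a fall and a modest rise could be displayed as no change.

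The shell also does not say whether a reactive but unconfirmed RPR counts towards the screening composite.

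**Working it through.** The documents contain no STI prevalence, no RPR reactivity rate and no LPUV attendance rate, so there is no planned figure to reproduce. The check asks what the shell would display if true prevalence did not change.

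**Inputs, all assumed:**
- c = prevalence of chlamydia, gonorrhoea or trichomonas, equal at both visits: 10%, 20%, 30%
- s = syphilis positivity at screening, independent of c: 0%, 1%, 3%, 5%
- m = share of the safety population with no STI test at LPUV: 0%, 5%, 10%, 20%, 30%

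**Formulas that follow from the shell:**
- Screening 'Any STI' = 1 − (1 − c)(1 − s)
- LPUV 'Any STI' = c(1 − m)

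**Results at c = 20%:**

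| s | m | Screening | LPUV | Apparent change |
|---|---|---|---|---|
| 0% | 0% | 20.0% | 20.0% | 0 |
| 0% | 10% | 20.0% | 18.0% | −2.0 points (denominator alone) |
| 3% | 0% | 1 − 0.80 × 0.97 = 22.4% | 20.0% | −2.4 points (syphilis alone) |
| 1% | 10% | 1 − 0.80 × 0.99 = 20.8% | 18.0% | −2.8 points |
| 3% | 10% | 22.4% | 18.0% | −4.4 points |
| 3% | 20% | 22.4% | 16.0% | −6.4 points |

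Across the whole grid the change runs from 0 (only when s = 0 and m = 0) to −12.5 points (c = 30%, s = 5%, m = 30%), and it is never positive. At the anticipated 1400 women, 22.4% against 18.0% is about 314 against 252 positives.

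**Could a rise be hidden?** With s = 3% and m = 10%, the LPUV composite equals the screening figure of 22.4% when true prevalence of the three organisms has risen to 22.4/0.9 = 24.9%, up from 20%. Without syphilis, the denominator alone would show a rise from 20% to 20/0.9 = 22.2% as flat. The single-organism rows carry only this second effect.

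**What could reverse the direction?** Footnote a dilutes screening too. If a share r of women have no screening STI result, screening becomes (1 − r)[1 − (1 − c)(1 − s)]. With c = 20% and m = 10%, the apparent fall vanishes at r = 1 − 18.0/20.8 = 13% (s = 1%) or r = 1 − 18.0/22.4 = 20% (s = 3%). Beyond that the table would show a rise.

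**After the change.** With the composite limited to the three organisms and women tested as the denominator, constant prevalence of 20% gives 20.0% at both visits, provided tested and untested women have the same prevalence.

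**The case against.** The strongest reply is that the direction is not fixed. Protocol sections 4.1 and 4.2 allow the IPM 027 LPUV to be combined with IPM 032 screening and enrolment if IPM 027 stops early. Only italicised steps are then required, and the STI swab and RPR steps do not appear to be italicised. SAP section 10.1 plans a subgroup of direct roll-overs, and the SAP does not say whether IPM 027 results fill their screening cells. This stands: a reader might infer that the table must show a spurious fall, and the documents do not support that.

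A reader might also infer that the table would conceal a rise in STIs during ring use. That goes too far. Chlamydia, gonorrhoea and trichomonas each have their own row at both visits. STIs are tabulated among the adverse events of special interest (SAP section 9.1), and Listing 16.2.8.8 gives results by visit. No change score, interval or test between visits is planned. SAP section 6.5 also expects women with STIs at screening to be treated and evaluated before or at enrolment, so a lower LPUV figure could be real and unrelated to the ring. These points limit the consequence. They leave the composite mismatch in place, and the organism rows share the denominator.

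Loss at LPUV is mitigated: early discontinuers are encouraged to have LPUV procedures, and a missed LPUV prompts testing at Exit. This makes m smaller but not zero, and SAP section 6.2 expects missed visits. The visit-level n (%) lines above 'Any STI' might be counts of women tested, which would let a reader rescale. The shell does not say so.

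Finally, testing for syphilis only at screening describes the schedule. Clinically indicated STI tests at other visits are allowed, so the LPUV syphilis row could hold a few results. It should not be read as a scheduled test, and those results should not be discarded.

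**Conclusion.** The point holds as one of comparability. As written, the shell sets a four-infection composite beside one that is, by schedule, three infections, and it counts women without a result as negative at either visit. The apparent change at LPUV could be a fall of about 0 to 6 points (c = 20%, s up to 3%, m up to 20%). That range rests on assumed rates and on syphilis being independent of the other infections; positive association would shrink the syphilis part. Missing screening results among direct roll-overs could cancel or reverse it, so neither the size nor the sign can be taken from the documents.

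The importance is minor. The table is descriptive, its components are shown, and other displays cover STIs. It is still worth correcting, because the remedy is cheap and the shells already use a better denominator elsewhere: Table 14.3.5.5 restricts its percentages to women with data.

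**What to change.** Edit Table 14.3.7.3 as follows:

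1. Define 'Any STI' as chlamydia, gonorrhoea or trichomonas at both visits.
2. Report syphilis separately at screening, with RPR reactive and confirmed on distinct rows.
3. Reconcile the LPUV TPHA/TPPA row with the test schedule. Keep any later, clinically indicated syphilis results in Listing 16.2.8.8.
4. Show the number tested at each visit and use it as the denominator for every row.
5. State whether an Exit Visit test that replaces a missed LPUV enters the LPUV block, and whether IPM 027 LPUV results fill the screening block for direct roll-overs.

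No new data are needed; the cost is a change to the shell and its footnotes. The one drawback is that a tested-only denominator assumes untested women resemble those tested, so the number not tested should be shown beside it.

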- **Table 14.7.10.2** will be similar to **Table 14.7.10.1** but the heading and analysis will be based on Any Timepoint

HIV-1 = Human immunodeficiency virus type 1; NNRTI = Non-nucleoside reverse transcriptase inhibitor ; NRTI = Nucleoside reverse transcriptase inhibitor; PI = Protease inhibitor
 Percentages are calculated out of the number of participants (per IPM 027 treatment) ^a In the virology population ^b Successful results

^c Resistance-associated mutations of interest not present in the data set are not included in the table

Resistance-associated mutations were defined using the Stanford HIV database algorithm Version 8.

Table 14.3.7.11
Data Overview of HIV-1 Seroconversion Timing Relative To HIV-1 RNA Detection and Treatment
Virology Population

Statistic	IPM 027 Dapivirine (N=XXX)	IPM 027 Placebo (N=XXX)	IPM 032 Overall (N=XXX)
First positive HIV-1 RNA Timing			
At time of seroconversion	n (%) ^a	X (X.X)	X (X.X)
Mutations detected before seroconversion	n (%) ^b	X (X.X)	X (X.X)
Mutations detected at seroconversion	n (%) ^b	X (X.X)	X (X.X)
Mutations detected after seroconversion	n (%) ^b	X (X.X)	X (X.X)
Before seroconversion			
At time of seroconversion	n (%) ^a	X (X.X)	X (X.X)
Mutations detected before seroconversion	n (%) ^b	X (X.X)	X (X.X)
Mutations detected at seroconversion	n (%) ^b	X (X.X)	X (X.X)
Mutations detected after seroconversion	n (%) ^b	X (X.X)	X (X.X)
Average days	Mean	XX.X	XX.X
Minimum and maximum days	(Min,Max)	(XX, XX)	(XX, XX)
IP use stopped			
At time of seroconversion	n (%) ^a	X (X.X)	X (X.X)
After seroconversion	n (%) ^a	X (X.X)	X (X.X)
Before seroconversion	n (%) ^a	X (X.X)	X (X.X)

Programmers Note: In case the date of last investigational product exposure (i.e. last ring removal) is missing, it is imputed with the last ring insertion date.

HIV-1 = Human immunodeficiency virus type 1

Percentages are calculated out of the number of participants (per IPM 027 treatment) ^a In the virology population ^b At the applicable visit

Table 14.3.7.12
 Overview of HIV-1 RNA and Genotyping Information Availability
 Virology Population

Statistic	IPM 027 Dapivirine (N=XXX)	IPM 027 Placebo (N=XXX)	IPM 032 Overall (N=XXX)
HIV-1 RNA for participants with HIV-1 seroconversion			
Participants with assessment prior to seroconversion	n (%) ^a	X (X.X)	X (X.X)
No HIV-1 RNA detected in any sample	n (%) ^b	X (X.X)	X (X.X)
HIV-1 RNA detected in at least 1 sample	n (%) ^b	X (X.X)	X (X.X)
Participants with assessment at time of seroconversion	n (%) ^a	X (X.X)	X (X.X)
Participants with assessment after seroconversion (on IP)	n (%) ^a	X (X.X)	X (X.X)
Participants with assessment after seroconversion (after IP)	n (%) ^a	X (X.X)	X (X.X)
Participants without assessment at time of seroconversion	n (%) ^a	X (X.X)	X (X.X)
Population-based sequencing			
Participants with assessment prior to seroconversion	n (%) ^a	X (X.X)	X (X.X)
Plasma HIV-1 RNA ≥2000 cop/mL	n (%) ^b	X (X.X)	X (X.X)
Plasma HIV-1 RNA <2000 cop/mL, ≥200 cop/mL	n (%) ^b	X (X.X)	X (X.X)
Participants with assessment at time of seroconversion	n (%) ^a	X (X.X)	X (X.X)
Plasma HIV-1 RNA ≥2000 cop/mL	n (%) ^b	X (X.X)	X (X.X)
Plasma HIV-1 RNA <2000 cop/mL, ≥200 cop/mL	n (%) ^b	X (X.X)	X (X.X)
Participants with assessment after seroconversion (on IP)	n (%) ^a	X (X.X)	X (X.X)
Plasma HIV-1 RNA ≥2000 cop/mL	n (%) ^b	X (X.X)	X (X.X)
Plasma HIV-1 RNA <2000 cop/mL, ≥200 cop/mL	n (%) ^b	X (X.X)	X (X.X)
Participants with assessment after seroconversion (after IP)	n (%) ^a	X (X.X)	X (X.X)
Plasma HIV-1 RNA ≥2000 cop/mL	n (%) ^b	X (X.X)	X (X.X)
Plasma HIV-1 RNA <2000 cop/mL, ≥200 cop/mL	n (%) ^b	X (X.X)	X (X.X)

HIV-1 = Human immunodeficiency virus type 1

Percentages are calculated out of the number of participants (per IPM 027 treatment) ^a In the virology population ^b With data ^c With a population-based sequencing assessment

Table 14.3.7.12
 Overview of HIV-1 RNA and Genotyping Information Availability
 Virology Population

Statistic	IPM 027 Dapivirine (N=XXX)	IPM 027 Placebo (N=XXX)	IPM 032 Overall (N=XXX)
Population-based sequencing			
Participants without assessment at time of seroconversion	n (%) ^a	X (X.X)	X (X.X)
HIV-1 Subtype			
A1	n (%) ^c	X (X.X)	X (X.X)
C	n (%) ^c	X (X.X)	X (X.X)
Etc.	n (%) ^c	X (X.X)	X (X.X)

HIV-1 = Human immunodeficiency virus type 1

Percentages are calculated out of the number of the number of participants (per IPM 027 treatment) ^a In the virology population ^b With ^c With a population-based sequencing assessment

Table 14.3.7.13.1
Summary of Mutational Patterns of Resistance-Associated Mutations at Seroconversion Timepoint
Virology Population

Subgroup: All IPM 032 participants		Statistic	IPM 027 Dapivirine (N=XXX)	IPM 027 Placebo (N=XXX)	IPM 032 Overall (N=XXX)
Resistance-Associated Mutation Combination					
Number of successful assessments	n (%) ^a		X (X.X)	X (X.X)	X (X.X)
NNRTI mutations					
None	n (%) ^a		X (X.X)	X (X.X)	X (X.X)
Any	n (%) ^b		X (X.X)	X (X.X)	X (X.X)
One	n (%) ^b		X (X.X)	X (X.X)	X (X.X)
Two	n (%) ^b		X (X.X)	X (X.X)	X (X.X)
Three	n (%) ^b		X (X.X)	X (X.X)	X (X.X)
...
Average	Mean		XX.X	XX.X	XX.X
NRTI mutations					
None	n (%) ^a		X (X.X)	X (X.X)	X (X.X)
Any	n (%) ^b		X (X.X)	X (X.X)	X (X.X)
One	n (%) ^b		X (X.X)	X (X.X)	X (X.X)
Two	n (%) ^b		X (X.X)	X (X.X)	X (X.X)
Three	n (%) ^b		X (X.X)	X (X.X)	X (X.X)
...
Average	Mean		XX.X	XX.X	XX.X
Major PI mutations					
None	n (%) ^a		X (X.X)	X (X.X)	X (X.X)
Any	n (%) ^b		X (X.X)	X (X.X)	X (X.X)
One	n (%) ^b		X (X.X)	X (X.X)	X (X.X)
Two	n (%) ^b		X (X.X)	X (X.X)	X (X.X)
Three	n (%) ^b		X (X.X)	X (X.X)	X (X.X)
...
Average	Mean		XX.X	XX.X	XX.X

Programmers Notes:

Please repeat table for the following subgroups: HIV-1 RNA level: HIV-1 RNA level: ≥ 2000 copies/mL, < 2000 copies/mL; HIV-1 subtype (C / Other) and Schedule A, B or C
- Table 14.3.7.13.2 will be similar to Table 14.3.7.13.1 but the heading and analysis will be based on Any Timepoint

HIV-1 = Human immunodeficiency virus type 1; NNRTI = Non-nucleoside reverse transcriptase inhibitor ; NRTI = Nucleoside reverse transcriptase inhibitor; PI = Protease inhibitor

Percentages are calculated out of the number of participants (per IPM 027 treatment) ^a In the virology population ^b Reported HIV-1 drug resistance-associated mutation

Resistance-associated mutations were defined using the Stanford HIV database algorithm Version 8.4

Table 14.3.7.14.1
Summary of Mutational Patterns of Resistance-Associated Mutations at Seroconversion Timepoint
Virology Population

Subgroup: All IPM 032 participants		IPM 027 Dapivirine (N=XXX)	IPM 027 Placebo (N=XXX)	IPM 032 Overall (N=XXX)
Mutation Score Classification	Statistic			
Resistance categorization score	N	XX	XX	XX
Susceptible				
Potential low-level resistant	n (%) ^a	X (X.X)	X (X.X)	X (X.X)
Low-level resistant	n (%) ^a	X (X.X)	X (X.X)	X (X.X)
Intermediate resistant	n (%) ^a	X (X.X)	X (X.X)	X (X.X)
High-level resistant	n (%) ^a	X (X.X)	X (X.X)	X (X.X)

Programmers Note:

Please repeat table for the following subgroups: HIV-1 RNA level: HIV-1 RNA level: \geq 2000 copies/mL, < 2000 copies/mL; HIV-1 subtype (C / Other); Schedule A, B or C
- Table14.3.14.2 will be similar to Table14.3.14.1 but the analysis and header will be based on Any Timepoint

HIV-1 = Human immunodeficiency virus type 1; NNRTI = Non-nucleoside reverse transcriptase inhibitor; NRTI = Nucleoside reverse transcriptase inhibitor; PI = Protease inhibitor

Percentages are calculated out of the number of (per IPM 027 treatment) ^aParticipants in the virology population ^bSuccessful assessments

Resistance-associated mutations were defined using the Stanford HIV database algorithm Version 8.4

Table 14.3.7.15
Timing Profile
Safety Population

Subgroup: All IPM 032 participants

Statistic	IPM 027			IPM 032		
	IPM 027 Dapivirine (N=XXX)	IPM 027 Placebo (N=XXX)	IPM 027 Overall (N=XXX)	IPM 027 Dapivirine (N=XXX)	IPM 027 Placebo (N=XXX)	IPM 032 Overall (N=XXX)
Time on randomized IP	n	XXX	XXX	XXX		
	Mean	XX.X	XX.X	XX.X		
	(q1,med,q3)	(XX.X,XX.X,XX.X)	(XX.X,XX.X,XX.X)	(XX.X,XX.X,XX.X)		
	SD	XX.XX	XX.XX	XX.XX		
	(Min, Max)	(XX, XX)	(XX, XX)	(XX, XX)		
Time on open-label IP	n	XXX				
	Mean	XX.X				
	(q1,med,q3)	(XX.X,XX.X,XX.X)				
	SD	XX.XX				
	(Min, Max)	(XX, XX)				
Total time on IP	n	XXX	XXX	XXX	XXX	XXX
	Mean	XX.X	XX.X	XX.X	XX.X	XX.X
	(q1,med,q3)	(XX.X,XX.X,XX.X)	(XX.X,XX.X,XX.X)	(XX.X,XX.X,XX.X)	(XX.X,XX.X,XX.X)	(XX.X,XX.X,XX.X)
	SD	XX.XX	XX.XX	XX.XX	XX.XX	XX.XX
	(Min, Max)	(XX, XX)	(XX, XX)	(XX, XX)	(XX, XX)	(XX, XX)

Programmers Note: Please repeat the table for the following subgroup: IPM 027 participants who directly enrolled in IPM 032. Note that the category 'Time off IP between IPM 027 and IPM 032' can be omitted for that subgroup.

HIV-1 = Human immunodeficiency virus type 1; IP = Investigational product

Table 14.3.7.15
Timing Profile
Safety Population

Subgroup: All IPM 032 participants

Statistic	IPM 027			IPM 032		
	IPM 027 Dapivirine (N=XXX)	IPM 027 Placebo (N=XXX)	IPM 027 Overall (N=XXX)	IPM 027 Dapivirine (N=XXX)	IPM 027 Placebo (N=XXX)	IPM 032 Overall (N=XXX)
Time off IP between IPM 027 and IPM 032	n			XXX	XXX	XXX
	Mean			XX.X	XX.X	XX.X
	(q1,med,q3)			(XX.X,XX.X,XX.X)	(XX.X,XX.X,XX.X)	(XX.X,XX.X,XX.X)
	SD			XX.XX	XX.XX	XX.XX
	(Min, Max)			(XX, XX)	(XX, XX)	(XX, XX)
Time to first positive HIV-1 RNA	n			XXX	XXX	XXX
	Mean			XX.X	XX.X	XX.X
	(q1,med,q3)			(XX.X,XX.X,XX.X)	(XX.X,XX.X,XX.X)	(XX.X,XX.X,XX.X)
	SD			XX.XX	XX.XX	XX.XX
	(Min, Max)			(XX, XX)	(XX, XX)	(XX, XX)
Time to seroconversion	n			XXX	XXX	XXX
	Mean			XX.X	XX.X	XX.X
	(q1,med,q3)			(XX.X,XX.X,XX.X)	(XX.X,XX.X,XX.X)	(XX.X,XX.X,XX.X)
	SD			XX.XX	XX.XX	XX.XX
	(Min, Max)			(XX, XX)	(XX, XX)	(XX, XX)

Programmers Note: Please repeat the table for the following subgroup: IPM 027 participants who directly enrolled in IPM 032. Note that the category 'Time off IP between IPM 027 and IPM 032' can be omitted for that subgroup.

HIV-1 = Human immunodeficiency virus type 1; IP = Investigational product

Table 14.3.7.16
Pregnancy Test Results
Safety Population

Subgroup: All IPM 032 participants

Visit	Pregnancy Result	Statistic	Centre 01			...	All Centres		
			IPM 027 Dapivirine (N=XXX)	IPM 027 Placebo (N=XXX)	IPM 032 Overall (N=XXX)		IPM 027 Dapivirine (N=XXX)	IPM 027 Placebo (N=XXX)	IPM 032 Overall (N=XXX)
Trial Month X / LPUV / All visits	Positive / Negative	n (%) ^a	X (X.X)	X (X.X)	X (X.X)	...	X (X.X)	X (X.X)	X (X.X)
		n (%) ^a	X (X.X)	X (X.X)	X (X.X)		X (X.X)	X (X.X)	X (X.X)

^aPercentages are calculated out of the number of participants in the safety population per centre and IPM027 treatment

Centre 01: Madibeng Centre for Research (MCR); Centre 02: MatCH Research Unit (MRU); Centre 04: Qhakaza Mbokodo (QM);

Centre 06: MRC/UVRI & LSHTM Uganda Research Unit (MRC/UVRI); Centre 07: Desmond Tutu HIV Foundation (DTHF), Masiphumelele; Centre 08: Ndlovu Care Group (NCG)

Table 14.3.8.1
Concomitant Medication
Safety Population

	Statistic	Centre 01 (N=XXX)	Centre 02 (N=XXX)	...	Centre 08 (N=XXX)	All Centres (N=XXX)
Participants with a reported concomitant medication	n (%) ^a	X (X.X)	X (X.X)	...	X (X.X)	X (X.X)
ATC Level 2 Preferred name	n (%) ^b	X (X.X)	X (X.X)	...	X (X.X)	X (X.X)
...						

Percentages are calculated out of the number of participants (by centre) ^a In the safety population ^b Reported concomitant medication

Concomitant medication is defined as any medication taken in conjunction with the investigational product (IP). This includes any medication that started after the first insertion of the IP, or started before the first insertion of the IP but ended on/after the first insertion of the IP.

Medications were coded using WHO DDE (version June 2017)

Centre 01: Madibeng Centre for Research (MCR); Centre 02: MatCH Research Unit (MRU); Centre 04: Qhakaza Mbokodo (QM);

Centre 06: MRC/UVRI & LSHTM Uganda Research Unit (MRC/UVRI); Centre 07: Desmond Tutu HIV Foundation (DTHF), Masiphumelele; Centre 08: Ndlovu Care Group (NCG)

Table 14.6.1
Participant Report, Feasibility of 3-Monthly Clinical Follow-Up Schedule
Safety Population

Visit Question of Interest Response	Statistic	Schedule A (N=XXX)	Schedule B (N=XXX)	Schedule C (N=XXX)	All Schedules (N=XXX)
Trial Month X					
Number of used/unused rings returned	m	XXX	XXX	XXX	XXX
Number of rings dispensed	M	XXX	XXX	XXX	XXX
The proportion of returned rings (used and unused) during the 3-monthly clinical follow-up schedule will also be reported	m/M	XX.X	XX.X	XX.X	XX.X
As per investigator decision are you coming to the research centre next month or in three months for your next visit?					
Next month	n (%) ^a	X (X.X)	X (X.X)	X (X.X)	X (X.X)
In three months	n (%) ^a	X (X.X)	X (X.X)	X (X.X)	X (X.X)
Will you take your extra rings with you today or will you come back to the research centre each month to pick up your new ring?					
Will take them all	n (%) ^a	X (X.X)	X (X.X)	X (X.X)	X (X.X)
Will leave them at the research centre to collect monthly	n (%) ^a	X (X.X)	X (X.X)	X (X.X)	X (X.X)
What are your reasons for leaving the rings at the research centre today?					
Do not want anyone to see the rings	n (%) ^a	X (X.X)	X (X.X)	X (X.X)	X (X.X)
Do not have a private place to store unused rings	n (%) ^a	X (X.X)	X (X.X)	X (X.X)	X (X.X)
Etc.	n (%) ^a	X (X.X)	X (X.X)	X (X.X)	X (X.X)
If you were not in a study, would you prefer to come to the health care clinic / provider for new rings each month, or every three months?					
Each month	n (%) ^a	X (X.X)	X (X.X)	X (X.X)	X (X.X)
Every three months	n (%) ^a	X (X.X)	X (X.X)	X (X.X)	X (X.X)
Don't mind	n (%) ^a	X (X.X)	X (X.X)	X (X.X)	X (X.X)
Depends	n (%) ^a	X (X.X)	X (X.X)	X (X.X)	X (X.X)
If you were not in a study, would you prefer to come to the health care clinic / provider for an HIV test each month, or every three months?					
Each month	n (%) ^a	X (X.X)	X (X.X)	X (X.X)	X (X.X)
Every three months	n (%) ^a	X (X.X)	X (X.X)	X (X.X)	X (X.X)
Don't mind	n (%) ^a	X (X.X)	X (X.X)	X (X.X)	X (X.X)
Depends	n (%) ^a	X (X.X)	X (X.X)	X (X.X)	X (X.X)

^a Percentages are calculated out of the number of participants in the safety population per visit schedule

Visit Schedule A = Participants attended trial month visit 1, 4, 7, 10, 13 and 16/Exit

Visit Schedule B = Participants attended trial month visit 1, 2, 5, 8, 11, 14 and 17/Exit

Visit Schedule C = Participants attended trial month visit 1, 2, 3, 6, 9, 12 and 15/Exit

Table 14.6.1
Participant Report, Feasibility of 3-Monthly Clinical Follow-Up Schedule
Safety Population

Visit Question of Interest Response	Statistic	Schedule A (N=XXX)	Schedule B (N=XXX)	Schedule C (N=XXX)	All Schedules (N=XXX)
Trial Month X					
Will you take your extra rings with you today or will you come back to the research centre each month to pick up your new ring?					
Will take them all	n (%) ^a	X (X.X)	X (X.X)	X (X.X)	X (X.X)
Will leave them at the research centre to collect monthly	n (%) ^a	X (X.X)	X (X.X)	X (X.X)	X (X.X)
What are your reasons for leaving the rings at the research centre today?					
Do not want anyone to see the rings	n (%) ^a	X (X.X)	X (X.X)	X (X.X)	X (X.X)
Do not have a private place to store unused rings	n (%) ^a	X (X.X)	X (X.X)	X (X.X)	X (X.X)
Etc.	n (%) ^a	X (X.X)	X (X.X)	X (X.X)	X (X.X)
If you were not in a study, would you prefer to come to the health care clinic / provider for new rings each month, or every three months?					
Each month	n (%) ^a	X (X.X)	X (X.X)	X (X.X)	X (X.X)
Every three months	n (%) ^a	X (X.X)	X (X.X)	X (X.X)	X (X.X)
Don't mind	n (%) ^a	X (X.X)	X (X.X)	X (X.X)	X (X.X)
Depends	n (%) ^a	X (X.X)	X (X.X)	X (X.X)	X (X.X)
If you were not in a study, would you prefer to come to the health care clinic / provider for an HIV test each month, or every three months?					
Each month	n (%) ^a	X (X.X)	X (X.X)	X (X.X)	X (X.X)
Every three months	n (%) ^a	X (X.X)	X (X.X)	X (X.X)	X (X.X)
Don't mind	n (%) ^a	X (X.X)	X (X.X)	X (X.X)	X (X.X)
Depends	n (%) ^a	X (X.X)	X (X.X)	X (X.X)	X (X.X)

^a Percentages are calculated out of the number of participants in the safety population per visit schedule

Visit Schedule A = Participants attended trial month visit 1, 4, 7, 10, 13 and 16/Exit

Visit Schedule B = Participants attended trial month visit 1, 2, 5, 8, 11, 14 and 17/Exit

Visit Schedule C = Participants attended trial month visit 1, 2, 3, 6, 9, 12 and 15/Exit

Table 14.6.1
 Participant Report, Feasibility of 3-Monthly Clinical Follow-Up Schedule
 Safety Population

Visit Question of Interest Response	Statistic	Schedule A (N=XXX)	Schedule B (N=XXX)	Schedule C (N=XXX)	All Schedules (N=XXX)
Trial Month X					
When you were doing your three monthly visits, did you take your extra rings with you or did you come back to the research centre each month to pick up your new ring?					
Always took them	n (%) ^a	X (X.X)	X (X.X)	X (X.X)	X (X.X)
Always left them at the research centre to collect monthly	n (%) ^a	X (X.X)	X (X.X)	X (X.X)	X (X.X)
Sometimes took them, sometimes left them at the research centre	n (%) ^a	X (X.X)	X (X.X)	X (X.X)	X (X.X)
What were your reasons for leaving the rings at the research centre?					
Did not want anyone to see the rings	n (%) ^a	X (X.X)	X (X.X)	X (X.X)	X (X.X)
Did not have a private place to store the unused rings	n (%) ^a	X (X.X)	X (X.X)	X (X.X)	X (X.X)
Etc.	n (%) ^a	X (X.X)	X (X.X)	X (X.X)	X (X.X)
If you were not in a study, would you prefer to come to the health care clinic / provider for new rings each month, or every three months?					
Each month	n (%) ^a	X (X.X)	X (X.X)	X (X.X)	X (X.X)
Every three months	n (%) ^a	X (X.X)	X (X.X)	X (X.X)	X (X.X)
Don't mind	n (%) ^a	X (X.X)	X (X.X)	X (X.X)	X (X.X)
Depends	n (%) ^a	X (X.X)	X (X.X)	X (X.X)	X (X.X)
If you were not in a study, would you prefer to come to the health care clinic / provider for an HIV test each month, or every three months?					
Each month	n (%) ^a	X (X.X)	X (X.X)	X (X.X)	X (X.X)
Every three months	n (%) ^a	X (X.X)	X (X.X)	X (X.X)	X (X.X)
Don't mind	n (%) ^a	X (X.X)	X (X.X)	X (X.X)	X (X.X)
Depends	n (%) ^a	X (X.X)	X (X.X)	X (X.X)	X (X.X)

^a Percentages are calculated out of the number of participants in the safety population per visit schedule

Visit Schedule A = Participants attended trial month visit 1, 4, 7, 10, 13 and 16/Exit

Visit Schedule B = Participants attended trial month visit 1, 2, 5, 8, 11, 14 and 17/Exit

Visit Schedule C = Participants attended trial month visit 1, 2, 3, 6, 9, 12 and 15/Exit

Table 14.6.2
Correlation Between Dapivirine Residual Levels (mg) and Results From Visual Inspection of Returned Vaginal Rings
Safety Population

Month Ring Used	Appearance	Statistic	White to Off-White	Slight Yellow to Yellow	Tan	Brown	Other
Trial month X / Exit visit	Used	n	XXX	XXX	XXX	XXX	XXX
		Mean	XX.X	XX.X	XX.X	XX.X	XX.X
		(q1,med,q3)	(XX.X,XX.X,XX.X)	(XX.X,XX.X,XX.X)	(XX.X,XX.X,XX.X)	(XX.X,XX.X,XX.X)	(XX.X,XX.X,XX.X)
		SD	XX.XX	XX.XX	XX.XX	XX.XX	XX.XX
		(Min, Max)	(XX, XX)	(XX, XX)	(XX, XX)	(XX, XX)	(XX, XX)
	Unused	n	XXX	XXX	XXX	XXX	XXX
		Mean	XX.X	XX.X	XX.X	XX.X	XX.X
		(q1,med,q3)	(XX.X,XX.X,XX.X)	(XX.X,XX.X,XX.X)	(XX.X,XX.X,XX.X)	(XX.X,XX.X,XX.X)	(XX.X,XX.X,XX.X)
		SD	XX.XX	XX.XX	XX.XX	XX.XX	XX.XX
		(Min, Max)	(XX, XX)	(XX, XX)	(XX, XX)	(XX, XX)	(XX, XX)
	Not sure	n	XXX	XXX	XXX	XXX	XXX
		Mean	XX.X	XX.X	XX.X	XX.X	XX.X
		(q1,med,q3)	(XX.X,XX.X,XX.X)	(XX.X,XX.X,XX.X)	(XX.X,XX.X,XX.X)	(XX.X,XX.X,XX.X)	(XX.X,XX.X,XX.X)
		SD	XX.XX	XX.XX	XX.XX	XX.XX	XX.XX
		(Min, Max)	(XX, XX)	(XX, XX)	(XX, XX)	(XX, XX)	(XX, XX)

Table 14.6.3
 Proportion of Participants Opting for HIV Rapid Tests at the Research Centre Between Scheduled 3-Monthly Visits
 Safety Population

	Statistic	IPM 032 Overall (N=XXX)
Number of participants with at least one HIV rapid test performed at an unscheduled visit	n (%) ^a	X (X.X)
Total number of participants with at least one HIV rapid test performed at any visit	n (%) ^a	X (X.X)
Proportion of participants undergoing HIV rapid tests at the research centre between scheduled 3-monthly follow up visits	p (%)	X.X (XX.X)

^a Percentages are calculated out of the number of participants in the safety population

p = (Number of participants with at least one HIV rapid test performed at an unscheduled visit) / (total number of participants with at least one HIV rapid test performed at any visit)

Table 14.6.4
Social Harms Report
Safety Population

	Statistic	IPM 032 Overall (N=XXX)
Participants who reported any social harm	n (%) ^a m	X (X.X) X
Responses by participants		
Has a similar event happened before?		
Yes	n (%) ^b m	X (X.X) X
No	n (%) ^b m	X (X.X) X
Not reported	n (%) ^b m	X (X.X) X
Due to trial involvement?		
Yes	n (%) ^b m	X (X.X) X
No	n (%) ^b m	X (X.X) X
Not sure	n (%) ^b m	X (X.X) X
Not reported	n (%) ^b m	X (X.X) X
Is the situation resolved?		
Yes	n (%) ^b m	X (X.X) X
No	n (%) ^b m	X (X.X) X
Not sure	n (%) ^b m	X (X.X) X
Not reported	n (%) ^b m	X (X.X) X
Impact on quality of life		
Minor disturbance	n (%) ^b m	X (X.X) X
Moderate disturbance	n (%) ^b m	X (X.X) X
Major disturbance	n (%) ^b m	X (X.X) X
Responses by research centre		
Type of social harm	n (%) ^b m	X (X.X) X
Physical	n (%) ^b m	X (X.X) X
Emotional	n (%) ^b m	X (X.X) X
Financial	n (%) ^b m	X (X.X) X
Not reported	n (%) ^b m	X (X.X) X

Percentages are calculated out of the number of participants ^a In the safety population ^b Reported social harm

Table 14.6.4
Social Harms Report
Safety Population

	Statistic	IPM 032 Overall (N=XXX)
Actions taken by participant		
None	n (%) ^b m	X (X.X) X
Sought support services	n (%) ^b m	X (X.X) X
Sought counseling	n (%) ^b m	X (X.X) X
Sought medical care	n (%) ^b m	X (X.X) X
Other	n (%) ^b m	X (X.X) X
Not reported	n (%) ^b m	X (X.X) X
Actions taken by research centre		
None	n (%) ^b m	X (X.X) X
Referred to support services	n (%) ^b m	X (X.X) X
Referred for counseling	n (%) ^b m	X (X.X) X
Medical care	n (%) ^b m	X (X.X) X
Other	n (%) ^b m	X (X.X) X
Not reported	n (%) ^b m	X (X.X) X
Resolution status		
Resolved	n (%) ^b m	X (X.X) X
Unresolved	n (%) ^b m	X (X.X) X
Ongoing at participant's last visit		

Percentages are calculated out of the number of ^a Participants in the safety population ^b Social harms reported

Table 14.6.5
 Participant Questionnaire – Part A (Month 1, 2, and 3)
 Safety Population

